8.1.3. Patient Global Assessment of Disease Activity VAS

The participant's overall assessment of his/her PsO and PsA activity will be recorded using the 100 mm horizontal VAS where the left end represents no disease activity, and the right end represents extreme disease activity.

8.1.4. Physician's Global Assessment of Disease Activity Visual Analog Scale

The Investigator will be asked to give an overall assessment of the severity of the participant's current PsO and PsA activity using a 100 mm horizontal VAS, where 0 represents no disease activity and 100 represents extremely active disease. The investigator making the assessment must be a rheumatologist or medically qualified physician. The same assessor should preferably perform the Physician's Global Assessment of Disease Activity VAS for a given participant particularly during the Induction Dosing Period (Period 2) to minimize interobserver variation.

8.2. Safety Assessments

Any clinically significant findings from physical examination, vital signs measurements, or laboratory measurements that result in a diagnosis and that occur after the participant receives the first dose of the study intervention should be reported to the Sponsor or its designee as an AE via eCRF.

Planned time points for all safety assessments are provided in the SoA (Section 1.3).

8.2.1. Physical Examinations

The complete physical examination (excluding pelvic, rectal, and breast examinations) will be performed according to the SoA (Section 1.3). This examination will determine whether the participant meets the criteria required to participate in the study and will also serve as a monitor for preexisting conditions and as a baseline for TEAE assessment. All physical examinations throughout the study should include an examination of the heart, lungs, and abdomen and a visual examination of the skin.

8.2.2. Vital Signs

For each participant, vital signs measurements should be conducted according to the SoA (Section 1.3).

Vital signs (sitting BP and pulse) and body temperature will be measured after resting for a minimum of 10 minutes at times indicated in the study schedule. At baseline (Week 0, Visit 2),

Week 12 (Visit 5), and Week 24 (Visit 6), sitting BP and pulse should be measured prior to administration of the investigational product and again approximately 1 hour after administration.

Any clinically significant findings from vital signs measurement that result in a diagnosis and that occur after the participant receives the first dose of the study intervention should be reported to the Sponsor or its designee as an AE via electronic data entry. Additional measurements of vital signs may be performed at the discretion of the investigator.

8.2.3. Electrocardiograms

For each participant, a 12-lead digital ECG will be collected locally only at screening visit according to the Study Schedule (Section 1.3). Participants must be supine for approximately 5 to 10 minutes before ECG collection and remain supine, but awake, during ECG collection.

Electrocardiograms will be interpreted by a qualified physician as soon after the time of ECG collection as possible, and ideally while the participant is still present, to determine whether the participant meets entry criteria and for immediate participant management, should any clinically relevant findings be identified. The qualified physician must document his/her review of the ECG at the time of evaluation.

The ECG will be maintained at the site and made available to the Sponsor as requested.

8.2.4. Evaluation of Disease Relapse

Patients will be assessed for the presence or absence of relapse at screening based on the following definitions:

a. Assessment of relapse for psoriasis participants:

Relapse is defined as worsening of psoriasis from the previous routine medical visit by 50% PASI or 1% BSA or sPGA ≥ 3 (Tian and Lai 2016).

If PASI, BSA, or sPGA are not available in medical report, relapse of psoriasis is defined as any worsening of psoriatic lesions that would, if persistent, in most cases require initiation or change of systemic therapy for psoriasis.

During the study period, relapse with ixekizumab would be defined as worsening of psoriasis from the previous visit by 50% PASI or 1% BSA or sPGA ≥ 3 .

Relapse present based on the above definition: Yes/No

Following details will be collected in addition in all PsO participants:

- Duration of the psoriasis since diagnosis:
- Duration of the psoriatic arthritis since diagnosis:
- Prior systemic medications used for psoriasis:
 - Name of the drug and dose
 - Start date
 - End date
- Prior systemic medications used for psoriatic arthritis:
 - Name of the drug and dose

- Start date
- End date

b. Assessment of relapse for psoriatic arthritis participants:

Relapse is defined as an increase in PsA disease activity from the previous routine medical records

- either DAS28 (erythrocyte sedimentation rate [ESR]) >2.6 and DAS28 (ESR) increase >0.6 or
- DAS28 (ESR) increase ≥ 1.2 , irrespective of absolute DAS28(ESR) (Emery et al. 2020; Helliwell et al. 2021).

If DAS-28 ESR is not available in medical records, relapse of PsA is defined as any increase in disease activity that would, if persistent, in most cases require initiation or change of systemic therapy for PsA.

Relapse present based on the above definition: Yes/No

Additionally, the following details will be collected in all PsA participants:

- Duration of the psoriasis since diagnosis:
- Duration of the psoriatic arthritis since diagnosis:
- Prior systemic medications used for psoriasis:
 - Name of the drug and dose
 - Start date
 - End date
- Prior systemic medications used for psoriatic arthritis:
 - Name of the drug and dose
 - Start Date
 - End date

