- Women who are infertile due to surgical sterilization (hysterectomy, bilateral oophorectomy, or tubal ligation) and congenital anomaly such as Müllerian agenesis.

[3] Have given written informed consent approved by Lilly, or its designee, and the Investigational Review Board (IRB)/ERB governing the site.

[4] Willing to self-administer study intervention.

For PsO Participants

[5] Present with chronic PsO based on a confirmed diagnosis of chronic PsO vulgaris for at least 6 months prior to baseline (Week 0; Visit 2).

[6] Have $\geq 10\%$ BSA of psoriasis at screening (Visit 1) and baseline (Week 0; Visit 2).

[7] Have both an sPGA score of ≥ 3 and PASI score ≥ 12 at screening (Visit 1) and baseline (Week 0; Visit 2).

- [8] Are a candidate for phototherapy and/or systemic therapy.

For PsA Participants

- [9] Have a diagnosis of active PsA for at least 6 months (based on a detailed medical history provided by the patient, and a physical exam by the Study Investigator, and/or other evidence such as that provided by joint x-rays, that establishes a history consistent with a diagnosis of active PsA of at least 6 months' duration) and currently meet the Classification for PsA (CASPAP) criteria (Section 10.6).
- [10] Have active PsA defined as the presence of at least 3/68 tender and at least 3/66 swollen joints, as determined by the Tender and Swollen Joint Count Assessment Form (Section 10.7) at Visit 1 (Screening) and Visit 2 (Week 0, baseline).
- [11] Presence of active PsO or a documented history of psoriasis.

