8.1.1.2. Static Physician Global Assessment

The sPGA is the physician's determination of the participant's psoriatic lesions, overall, at a given time point. The sPGA is recommended as an endpoint to assess efficacy in the treatment of PsO/PsA (EMA 2004). Overall, lesions are categorized by descriptions for induration, erythema, and scaling. For the analysis of responses, the participant's PsO/PsA is assessed as clear (0), minimal (1), mild (2), moderate (3), severe (4), or very severe (5).

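### Does the loosely worded sPGA arm of psoriasis relapse, with a PsA rule that needs an unscheduled ESR, call for a change to Section 8.2.4?

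*Protocol*

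**What the plan says.** Section 8.2.4 gives one relapse rule per indication, each answered Yes or No.

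- **Psoriasis, at screening.** Relapse is "worsening of psoriasis from the previous routine medical visit by 50% PASI or 1% BSA or sPGA", followed by a threshold of 3 or more. A clinical-judgement fallback applies in this case: "If PASI, BSA, or sPGA are not available in medical report".
- **Psoriasis, on study.** The same three arms are repeated against the preceding study visit: "During the study period, relapse with ixekizumab would be defined as worsening of psoriasis from the previous visit by 50% PASI or 1% BSA", again with the sPGA threshold of 3.
- **PsA.** "Relapse is defined as an increase in PsA disease activity from the previous routine medical records". Two limbs follow. The first is a DAS28(ESR) above 2.6 with an increase of more than 0.6. The second is an increase of at least 1.2, "irrespective of absolute DAS28(ESR"). A similar clinical fallback opens with "If DAS-28 ESR is not available in medical records".

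Inclusion criterion [7] (Section 5.1) begins "Have both an sPGA score of" 3 or more, and it applies at both screening and baseline. Section 8.1.1.2 gives the sPGA scale: "clear (0), minimal (1), mild (2), moderate (3), severe (4), or very severe (5").

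The Schedule of Activities (Section 1.3) marks the relapse evaluation at Visit 1 only. The summary of changes says it was added at screening on the recommendation of the Subject Expert Committee.

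**The concern.** The first two psoriasis arms are amounts of worsening. The third has the form of an entry threshold. If it is a level, it is true of every psoriasis participant who qualifies for the trial and is judged by this rule, including someone who has improved from 5 to 3, so the item would carry no information. If it is a change, the protocol does not say which: any worsening that ends at 3 or above, a crossing from below 3, or a rise of 3 points. Two sites could then code the same patient differently.

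For PsA, both limbs are increases, so a current DAS28(ESR) is needed beside the earlier one. ESR is not scheduled, and the fallback is worded for a value missing from the medical records. A participant with an earlier value on file and no current one seems to fall between the two.

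At stake is a data item that was added on an expert committee's recommendation and might not be coded reproducibly.

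**Working it through.** **1. How far the readings differ.** The plan states no figure here, so the check is an enumeration. Inputs: previous sPGA *p* from 0 to 5 (Section 8.1.1.2) and current sPGA *c* from 3 to 5 (inclusion [7]), giving 6 × 3 = 18 pairs.

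| Reading of the sPGA arm | Rule | Relapse, of 18 | 5→3 | 3→4 | 2→3 | 0→3 |
|---|---|---|---|---|---|---|
| Level | c ≥ 3 | 18 | Yes | Yes | Yes | Yes |
| Any worsening ending at 3 or more | c > p and c ≥ 3 | 3 + 4 + 5 = 12 | No | Yes | Yes | Yes |
| Crossing | p < 3 and c ≥ 3 | 3 × 3 = 9 | No | No | Yes | Yes |
| Rise of 3 points or more | c − p ≥ 3 | 1 + 2 + 3 = 6 | No | No | No | Yes |

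The sums run over c = 3, 4, 5. The readings are nested, so once the level reading is set aside the other three disagree on 12 − 6 = 6 pairs: 1→3, 2→3, 2→4, 3→4, 3→5 and 4→5. The pairs are counted equally and say nothing about how often each occurs.

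**2. What the recorded answer depends on.** The form records one Yes or No for three arms joined by *or*. The sPGA term matters only when the PASI and BSA arms are both unmet. The BSA arm is a low bar, at 1%, in participants who must have at least 10% BSA involved (inclusion [6]). The sPGA grades induration, erythema and scaling rather than extent, so the arms need not move together and some dependence on the sPGA term remains. The documents do not allow its share to be estimated. Participants without earlier scores take the clinical fallback and are untouched.

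**3. ESR.** Appendix 2 lists 7 haematology items plus 6 absolute counts, 13 in all, and ESR is not among them. The Schedule of Activities has no ESR row either. The protocol gives no DAS28(ESR) formula. Assuming the same four components as DAS28-CRP in Section 8.1.2 with ESR in place of CRP, the tender and swollen joint counts are scheduled at Visit 1, the patient global VAS starts at Week 0, and ESR is never scheduled. Two of four inputs are therefore available at the visit where relapse is judged. Appendix 2 lets the investigator order additional tests.

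**4. Where the answer is used.** Relapse is not among the primary or secondary endpoints (Section 3), the eligibility criteria (Sections 5.1 and 5.2), or the analyses visible in Section 9. The on-study definition has no evaluation scheduled after Visit 1. PASI, BSA and sPGA are scheduled at Weeks 4, 8, 12 and 24 and at early termination, so on-study relapse could be derived later if a meaning is fixed.

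**The case for a change.** The strongest case for a change is that the item answers a committee's recommendation and should mean the same at every site. Rejecting the level reading does not rescue the wording, because three change readings remain and disagree on 6 of 18 pairs. The psoriasis fallback covers missing scores, not an unclear rule. DAS28-CRP cannot stand in at Visit 1, since hs-CRP and the patient global VAS begin at Week 0. Discretionary testing does not make a rule uniform. The repair would be a few words, with no new test or visit.

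Most of that stands as description. The sPGA term is unclear, and the PsA fallback is silent on a missing current value. Three parts do not carry the weight put on them. The reading that makes the item empty requires ignoring that the sentence is about worsening since the previous visit; an improvement from 5 to 3 cannot sensibly be called that. The enumeration scores one arm of three, so it does not show that the recorded answer would change. And the PsA fallback is not limited to the earlier value: a site that holds no current DAS28(ESR) can reasonably apply it.

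**Conclusion.** The textual observations are right, but they do not call for a change to the plan. If Section 8.2.4 is followed exactly as written, the primary adverse event summaries, PASI 75 and sPGA (0,1) at Week 12, and ACR20 at Week 24 are all unaffected, because none of them draws on the relapse answer. What remains is a baseline descriptor that may be coded unevenly in psoriasis participants who have earlier scores on file and meet neither the PASI nor the BSA arm, and in PsA participants with an earlier DAS28(ESR) but no current one. Neither group can be counted from the protocol.

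The meaning of the sPGA term is for the sponsor to state, and completion guidance for the form is a sufficient place to do so. The PsA gap is one that sites can fill through the fallback or an extra test. Whether on-study relapse is reported is ordinarily settled in the SAP.

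This rests on two assumptions: that no redacted exploratory endpoint or analysis uses relapse, and that the item stays a screening descriptor. If relapse became an outcome or a subgroup factor, the sPGA wording would have to be settled first.

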8.2.5. Clinical Safety Laboratory Tests

See Appendix 10.2 for the list of clinical laboratory tests to be performed by a Lilly-designated or local laboratory and the SoA (Section 1.3) for the timing and frequency.

The investigator must review the laboratory results, document this review, and report any clinically relevant changes occurring during the study as an AE. The laboratory results must be retained with source documents unless a Source Document Agreement or comparable document cites an electronic location that accommodates the expected retention duration. Clinically significant abnormal laboratory findings are those which are not associated with the underlying disease, unless judged by the investigator to be more severe than expected for the participant's condition.

All laboratory tests with values considered clinically significantly abnormal during participation in the study or within a time period equivalent to the maximum 5 half-lives of active interventions after the last dose of study intervention should be repeated until the values return to normal or baseline or are no longer considered clinically significant by the investigator or medical monitor.

- If such values do not return to normal/baseline within a period of time judged reasonable by the investigator, the etiology should be identified, and the Sponsor notified.
- All protocol-required laboratory assessments, as defined in Appendix 10.2, must be conducted in accordance with the SoA (Section 1.3), standard collection requirements, and applicable study laboratory manual.

If laboratory values from non-protocol specified laboratory assessments performed at an investigator-designated local laboratory require a change in participant management or are considered clinically significant by the investigator (e.g., SAE or AE or dose modification), then report the information as an AE.

8.2.6. Pregnancy Testing

See the SoA (Section 1.3) for frequency of pregnancy testing and Appendix 10.2 for additional details about these tests.

At screening

Serum pregnancy tests will be given prior to the first dose of the study intervention for females ≥ 10 years of age (< 10 years at investigator discretion) if menarche has been reached or if there is reason to believe the participant is sexually active. Pregnancy test results at screening must be known prior to first dose of the study intervention.

During the induction dosing and maintenance period

Female participants of childbearing potential (age 10 and older if menarche has been reached or if there is reason to believe the participant is sexually active, or younger participants per investigator assessment of sexual maturity) will undergo a urine pregnancy test at the clinic on a quarterly basis during scheduled regular visits through Week 156 or the ETV. Additional urine pregnancy testing may be performed at the investigator's discretion. Participants determined to be pregnant will be discontinued from treatment and will no longer be administered study intervention (see Section 7.1.1).

During the post-treatment follow-up period

As indicated in the SoA (Section 1.3), urine pregnancy tests will be collected during each of the post-treatment follow-up visits.

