1.3. Schedule of Activities (SoA)

Table RHCZ.1.1. Schedule of Activities

	Screening (Period 1)	Induction Dosing (Period 2)				Maintenance (Period 3)		Post Treatment Follow-Up (Period 4)	
		Baseline							As Needed
CRF Visit Number	V1	V2	V3	V4	V5	V6	ETV	V801	V802
Study Week		W0	W4	W8	W12	W24		LV + W4	LV + W8
Study Days	-28 to -5 d	0 d	28 ± 3 d	56 ± 3 d	84 ± 3d	168 ± 5 d		± 4 d	± 4 d
Informed consent	X								
Complete medical history	X								
Demographics ^a	X								
Substance use (alcohol, caffeine, tobacco use)	X								
Electrocardiogram	X								
Evaluation for disease relapse ^b	X								
Physical examination ^c	X								
Weight	X	X				X	X	X	
Height		X							
Body mass index		X							
Inclusion/exclusion criteria ^d	X	X							
Vital signs	X	X				X	X	X	X
Concomitant medications	X	X	X	X	X	X	X	X	X
Review preexisting conditions/AEs	X	X	X	X	X	X	X	X	X
Administer study intervention ^e		X	X	X	X				
Dispense study drug		X	X	X	X				
Study drug compliance ^f		X	X	X	X				
Dispense Study Intervention Administration Log		X	X	X	X				
Collect, review, and enter data from Study Intervention Administration Log			X	X	X	X	X		

Schedule of Activities

	Screening (Period 1)	Induction Dosing (Period 2)				Maintenance (Period 3)		Post Treatment Follow-Up (Period 4)		
		Baseline						As Needed		
CRF Visit Number	V1		V2	V3	V4	V5	V6	ETV	V801	V802
Study Week		W0		W4	W8	W12	W24		LV + W4	LV + W8
Study Days	-28 to -5 d	0 d		28 ± 3 d	56 ± 3 d	84 ± 3d	168 ± 5 d		± 4 d	± 4 d
Efficacy Measures										
Clinician-Rated or -Administered Assessments										
PAS ^{fg}	X	X	X	X	X	X	X			
BSA ^g	X	X	X	X	X	X	X			
sPGA ^g	X	X	X	X	X	X	X			
TJC/SJC (68/66 joints) ^h	X	X	X	X	X	X	X			
PGA Disease Activity VAS ^h		X	X	X	X	X	X			
Patient-Rated Assessments										
Patient Assessment of Pain VAS ⁱ		X	X	X	X	X	X			
Patient Global Assessment Disease Activity VAS		X	X	X	X	X	X			
HAQ-DI ⁱ		X	X	X	X	X	X			
Laboratory Tests										
Chest x-ray (local) ^j	X					X	X			
Administer Mantoux TB test/QuantiFERON®-TB Gold ^k	X					X	X			
HIV/HCV	X									
HBV ^l	X	X			X	X	X		X	
Serum pregnancy test ^m	X									
Urine pregnancy test ⁿ		X	X	X	X	X	X			
Serum chemistry	X	X				X	X	X		

Schedule of Activities

	Screening (Period 1)	Induction Dosing (Period 2)					Maintenance (Period 3)		Post Treatment Follow-Up (Period 4)	
										As needed
		Baseline								
CRF Visit Number	V1	V2	V3	V4	V5	V6	ETV	V801	V802	
Study Week		W0	W4	W8	W12	W24		LV + W4	LV + W8	

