4.1.4. Post-Treatment Follow-Up Period (Period 4)

All participants receiving at least 1 dose of study intervention will enter the Post-Treatment Follow-Up Period (Period 4) for a minimum of 4 weeks, beginning after their last regularly scheduled visit at Week 24 (or the date of their ETV).

Required study visits should occur at 4 weeks (Visit 801) after the last regularly scheduled visit at Week 24 (or the date of the participant's ETV), except for participants with a concurrent infection that requires systemic anti-infective therapy (described below).

If, at Visit 801, a participant's neutrophil count is ≥ 1500 cells/ μ L or greater than or equal to the participant's baseline neutrophil count, the participant's participation in the study will be considered complete unless the investigator determines additional follow-up may be necessary. An additional study visit (Visit 802) 8 weeks after Visit 801 may be required for appropriate participant management (described below).

If, at the last scheduled visit or ETV, a participant's neutrophil count is < 1500 cells/ μ L ($< 1.50 \times 10^3/\mu$ L or < 1.50 GI/L) and less than the participant's baseline neutrophil count, the following measures should be taken:

- Participants with concurrent infection: If there is a concurrent infection that requires systemic anti-infective therapy, the participant should receive appropriate medical care and a repeat test for neutrophil count should be performed at least Q4W (or sooner as appropriate) until resolution of infection. Upon resolution of infection, the neutrophil count should be monitored using the required study visits in the Post-Treatment Follow-Up Period (Period 4) design at Visits 801 (4 weeks after resolution of infection) and 802 (8 weeks after Visit 801); additional visits may be required depending on the degree of neutropenia.
- Participants without concurrent infection: If there is no concurrent infection that requires systemic anti-infective therapy, the neutrophil count should be monitored using the required study visits in the Post-Treatment Follow-Up Period (Period 4) design, Visits 801 (4 weeks post- ETV or last regularly scheduled visit at Week 24) and 802 (if necessary); additional visits may be required depending on the degree of neutropenia.
- For Visit 801 and subsequent visits, the following monitoring applies:

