5.1. Inclusion Criteria

Participants are eligible to be included in the study only if all of the following criteria apply:

- [1] Are male or female patients 18 years or older and are of ≥ 50.0 kg weight.
- [2] Male or nonpregnant, nonbreastfeeding female participants.

Participants of child-bearing potential who are abstinent (if this is complete abstinence, as their preferred and usual lifestyle).

Total abstinence is defined as refraining from intercourse during the entirety of the study and for at least 12 weeks following the last dose of ixekizumab. Periodic abstinence such as calendar, ovulation, symptothermal, post-ovulation methods, and withdrawal are not acceptable methods of contraception.

Otherwise, participants and their partners of childbearing potential must agree to use 2 effective methods of contraception, where at least 1 form is highly effective for the entirety of the study and for at least 12 weeks following the last dose of ixekizumab.

The following contraception methods are considered acceptable (the participant, and their partner, should choose 2, and 1 must be highly effective [defined as <1% failure rate per year when used consistently and correctly]):

- Highly effective birth control methods:

- Combined (estrogen- and progestogen-containing) hormonal contraception associated with inhibition of ovulation: oral, intravaginal, or transdermal;
- Progestogen-only hormonal contraception associated with inhibition of ovulation: oral, intravaginal, or implantable;
- Intrauterine device/intrauterine hormone releasing system;
- Vasectomized partner (with appropriate post-vasectomy documentation of the absence of sperm in the ejaculate).
- Effective birth control methods:
 - Male or female condom with spermicide (it should be noted that the use of male and female condoms as a double barrier method is not considered acceptable due to the high failure rate when these methods are combined).
 - Diaphragm with spermicide.
 - Cervical sponge.
 - Cervical cap with spermicide.

Note: When local guidelines concerning highly effective or effective methods of birth control differ from the above, the local guidelines must be followed.

Adolescent females who have started menses (even 1 cycle and any amount of spotting) are considered to be of childbearing potential.

Women of nonchildbearing potential are not required to use birth control and they are defined as:

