7.1. Discontinuation of Study Intervention

Study intervention may be temporarily withheld or permanently discontinued during the study.

Participants who permanently discontinue study intervention early will undergo early termination procedures, which include:

- an ETV, and
- PTFU visits (V801 and V802).

The investigator will complete any AE reporting and follow-up (Section 8.3).

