7.3. Lost to Follow up

A participant will be considered lost to follow-up if he/she repeatedly fails to return for scheduled visits and is unable to be contacted by the study site. Site personnel or designee are

expected to make diligent attempts to contact participants who fail to return for a scheduled visit or were, otherwise, unable to be followed up by the site.

Site personnel, or an independent third party, will attempt to collect the vital status of the participant within legal and ethical boundaries for all participants enrolled, including those who did not get investigational product. Public sources may be searched for vital status information. If vital status is determined to be deceased, this will be documented, and the participant will not be considered lost to follow-up.

The Sponsor personnel will not be involved in any attempts to collect vital status information.

8. Study Assessments and Procedures

Study procedures and their timing are summarized in the SoA (Section 1.3).

Immediate safety concerns should be discussed with the Sponsor immediately upon occurrence or awareness to determine if the participant should continue or discontinue study intervention.

Adherence to the study design requirements, including those specified in the SoA, is essential and required for study conduct.

All screening evaluations must be completed and reviewed to confirm that potential participants meet all eligibility criteria. The investigator will maintain a screening log to record details of all participants screened and to confirm eligibility or record reasons for screening failure, as applicable.

The joint assessor (or designee) should be a rheumatologist, trained dermatologist or skilled joint assessor and will be responsible for completing the joint counts for swelling, tenderness, and limited range of motion. Additionally, the assessor will perform the following assessments: Physician's Global Assessment of Disease Activity, PASI, BSA.

To ensure consistent skin and/or joint evaluation throughout the study, individual participants should be evaluated by the same assessor for all study visits whenever possible.

Investigators or relevant clinical staff will provide age-appropriate explanations to all study participants prior to any assessment or procedure.

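### Section 8.2.6 requires a urine pregnancy test at every follow-up visit and cites the SoA for it, but the SoA schedules none; its quarterly, Week 156 rule does not fit this trial either

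*Protocol*

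**What the plan says.** Section 8.2.6 opens by sending the reader to the SoA for the frequency of pregnancy testing. For the treatment periods it then sets clinic urine tests "on a quarterly basis during scheduled regular visits through Week 156 or the ETV". For the post-treatment period it says: "As indicated in the SoA (Section 1.3), urine pregnancy tests will be collected during each of the post-treatment follow-up visits".

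In the SoA (Section 1.3), the row "Urine pregnancy test" is marked at V2 to V6 (Weeks 0, 4, 8, 12 and 24) and at the ETV. The V801 and V802 cells are empty. The footnote to the row limits the test to females of childbearing potential and adds no follow-up test.

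The opening of Section 8 gives the SoA binding force: "Adherence to the study design requirements, including those specified in the SoA, is essential and required for study conduct". Section 8.2.5 likewise ties protocol-required laboratory assessments to the SoA, and Appendix 2 (Section 10.2) lists the pregnancy tests among the laboratory tests. Footnote e of that appendix adds monthly home urine tests between visits, ending at Week 24.

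**The concern.** The follow-up sentence attributes to the SoA something the SoA does not contain, so a site cannot satisfy both. One that schedules from the SoA does no follow-up test, while one that works from Section 8.2.6 does one or two.

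The test falls in a period that still matters for pregnancy. The last dose is at Week 20 (Section 6.6), and Section 5.1 requires contraception "for at least 12 weeks following the last dose of ixekizumab". V801 lies inside that window. Section 8.3.2 requires information on any pregnancy that occurs during participation. Without a test at V801, a conception too recent to show at Week 24, or one during follow-up, may go undetected before the participant leaves the study.

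The treatment-period sentence has a separate fault: this trial has no Week 156, and the SoA tests at every treatment visit instead of quarterly.

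**Working it through.** The plan gives no figure to reproduce. The check sets the text against the table and then does the visit arithmetic.

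**Counting the SoA row.** The visit columns are V1, V2, V3, V4, V5, V6, ETV, V801 and V802. The urine row has an empty V1 cell, six marks (V2, V3, V4, V5, V6, ETV) and nothing after. Section 8.2.6 would need eight marks. Lost columns in the PDF reading do not explain the gap: the Hematology row of the same table carries marks at V801 and V802, and the SoA copy in Appendix 8 (Section 10.8) shows the same six urine marks.

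**Inputs.** Week 24 is Day 168 and V801 is the last visit + 4 weeks, ±4 days (SoA). V802 is the last visit + 8 weeks (SoA) or 8 weeks after V801 (Section 4.1.4). The last dose is at Week 20, Day 140 (Section 6.6). Contraception runs for at least 12 weeks after it (Section 5.1).

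**Completer.** If the neutrophil criterion in Section 4.1.4 is met at V801, "participation in the study will be considered complete unless the investigator determines additional follow-up may be necessary".
- Last scheduled test by the SoA: Day 168 (Week 24).
- Last scheduled test by Section 8.2.6: 168 + 28 = Day 196 (Week 28).
- Difference: 28 days, or 28 − 4 = 24 to 28 + 4 = 32 days with the V801 window.
- End of required contraception: 140 + 84 = Day 224 (Week 32), so V801 falls 224 − 196 = 28 days before it ends.
- The home tests of Appendix 2 stop at Week 24 and do not fill the gap.

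**Early discontinuer.** Section 7.1 lists both follow-up visits, while the SoA heads V802 as needed. The last test by the SoA is at the ETV. By Section 8.2.6, tests follow at ETV + 28 days and, if V802 is held, at ETV + 56 days (SoA timing) or ETV + 28 + 56 = ETV + 84 days (Section 4.1.4 timing).

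| Follow-up urine tests required | SoA | Section 8.2.6 |
|---|---|---|
| Participation ends at V801 | 0 | 1 |
| V802 also held | 0 | 2 |

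**Treatment-period wording.** The SoA intervals are 4, 4, 4 and 12 weeks, so only the last is quarterly. Week 156 lies 156 − 24 = 132 weeks after the last treatment visit.

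**The case against.** The strongest reply is that the sentence in Section 8.2.6, not the SoA, may be the mistake. The section defers to the SoA for frequency, Section 4.1 says the SoA gives the procedures and their timing, and home testing also stops at Week 24. The section plainly was not fitted to this trial: besides Week 156, it gives testing rules for girls aged 10 and younger, although inclusion criterion 1 requires age 18 or older. On that reading the sentence should be deleted and no tests added. This stands in part: deletion would also make the two places agree. It does not rescue the current text, which is wrong either way.

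A second reply is that requiring adherence to the SoA does not cancel the body text, so some sites would test. That is fair, but it means practice may differ between sites, which is itself the problem.

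Third, the quarterly wording is a weak conflict, because the SoA never leaves more than 12 weeks between treatment-period tests, and no visit exists at which the Week 156 rule could be carried out. This is accepted; that part is editorial.

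Fourth, the stake is small. Dosing has ended, so no dosing decision depends on the result. Adverse event review continues at V801 and V802, investigators may test at their discretion, and known pregnancies are reported within 24 hours. All true. However, discretionary testing does not replace a required test, and reporting applies only to pregnancies that come to light.

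**Conclusion.** The point holds. Section 8.2.6 is wrong as written: it cites the SoA for follow-up tests that the SoA does not schedule. For a completer who ends at V801, the difference is one test and 28 days (24 to 32 with the visit window). For anyone who also attends V802, it is two tests. Only women of childbearing potential are affected, and no endpoint, analysis population or estimate changes. The Week 156 phrase is a wording error with no practical effect.

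The figures assume visits on their nominal days and, for the completer, a last dose at Week 20. The protocol does not say that testing must cover the whole contraception window. Even under Section 8.2.6, Weeks 28 to 32 have no scheduled test unless V802 is held.

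**What to change.** In the SoA, mark the urine pregnancy test at V801 and, when that visit is held, at V802. In Section 8.2.6, replace the quarterly, Week 156 wording with clinic testing at each visit marked in the SoA through Week 24 or the ETV.

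Adding the marks is preferable to deleting the sentence: it carries out the only explicit instruction the protocol gives for follow-up, and V801 falls while contraception is still required. If the sponsor intends no follow-up testing, the sentence must be removed instead.

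The cost is two table marks, one change of wording, and one or two urine tests per woman of childbearing potential at visits already held.
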